### 8.1.2. Sensitivity Analysis

#### *Sensitivity analysis based on rescue medication with 28-day effective window:*

The primary analysis will be repeated applying a 28-day window on rescue medication. Specifically, if a patient meets platelet response definition before a rescue therapy or after 28 days since a use of rescue medication, the patient will be considered as a responder.

The same analysis on ORR including summary statistics and logistic regression described in the primary analysis above will be carried out.

#### *Sensitivity analysis based on treatment-policy strategy:*

The primary analysis will be repeated on assessments in all scheduled visits from post-baseline until Week 12, regardless of patients using rescue medication or discontinuation. The missing platelet count values will be imputed by Multiple Imputation (MI) method for all treatment groups, under the missing at random (MAR) framework.

The SAS procedure MI will be used to impute missing platelet count at the scheduled analysis visits (up to Week 12) to create 25 complete data sets. The missing data patterns

will be checked by treatment and at the scheduled visits for the platelet count. If there are non-monotone missing patterns, two separate imputation procedures will be used to complete the imputation process.

In the first step, the Markov Chain Monte Carlo (MCMC) method will be used to impute missing values by treatment to create 25 imputed data sets with monotone missing patterns. The seed will be set to 7032101, the imputed values will be rounded to 3 decimals with  $10^9/L$  unit and a single chain will be used to produce imputations.

In the second step, the monotone regression method will be used to impute the remaining missing values for the 25 data sets with monotone missing patterns. The MONOTONE REG statement will be used with seed 2101703. The missing values at each visit will be imputed based on treatment, values at baseline and previous visits, and prior TPO-receptor agonist use.

If model fail to converge because the number of visits is more than number of subjects, the model will be reformed. The nearest visits (Week 1 Day 1 to Week 2 Day 8, Week 3 to Week 7, and Week 9 to Week 12) will be imputed by two steps imputation procedures described above separately with unique seed. For visits Week 1 Day 1 to Week 2 Day 8, the seed used in first step is 7032101 and in second step is 2101703. For visits Week 3 to Week 7, the seed used in first step is 1021984 and in second step is 1984102. For visits Week 9 to Week 12, the seed used in first step is 1072018 and in second step is 2018107.

After the completion of two steps imputations, the response will be defined based on platelet counts in the 25 complete datasets and the same logistic regression model described in [Section 8.1.1](#) will be used to analyze the 25 complete datasets. The SAS procedure MIANALYZE will be used to combine the results for the statistical inferences.

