## 3.2. Study Endpoints

### 3.2.1. Primary Endpoint

The primary endpoint, patient platelet response, is defined as platelet count  $\geq 30,000/\mu\text{L}$  and doubling the baseline (average of 2 previous counts), at any visit during the treatment period and without the use of rescue medication. Refer baseline definition to Section 4.2.

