### 8.1. Primary Efficacy Endpoint

The primary efficacy endpoint, patient platelet response, is defined as platelet count  $\geq$  30,000/ $\mu$ L and doubling the baseline (average of 2 previous counts), at any visit during the treatment period and without a use of rescue medication. Refer baseline definition to Section 4.2. The average based on last 2 platelet counts at the time of evaluation.

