#### *Sensitivity analysis based on hypothetical strategy*

The primary analysis will be repeated based on a hypothetical scenario if the rescue medication had not occurred. Specifically, applying the same rescue medication window, all assessments happened within 28 days of the use of rescue medication will be considered as missing, regardless if they are collected or not. Then all missing data will be imputed until Week 12 by Multiple Imputation (MI) method for all treatment groups, under:

- Missing at random (MAR) framework:  
Under this framework, the same MI method will be applied as outlined in [Section 8.1.2](#).
- Missing not at random (MNAR) framework:

Two imputation steps will be performed under this assumption. First step for arbitrary missing is MCMC monotone imputation which is the same as described in Section 8.1.2. The second step is control-based pattern imputation using monotone regression method with seed 2010703, in which the missing data in all active treatment groups and placebo group will be imputed based on placebo group using the neighboring-case missing values method with k=2.

If model fail to converge because the number of visit is more than number of subjects, the same approach in [Section 8.1.2](#) will be applied. When imputed value out of range (ie value <0), the value will be replaced by min value in dataset.

The same ANCOVA model defined in primary analysis will be carried out to analyze the 25 complete datasets. The SAS procedure MIANALYZE will be used to combine the results for the statistical inferences

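### The treatment-policy analysis of platelet response imputes raw counts with normal models and then applies an any-visit threshold, so it classes some non-responding dropouts as responders in every arm

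*SAP*

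**What the plan says.** The treatment-policy sensitivity analysis in SAP 8.1.2 imputes missing platelet counts up to Week 12 under missing at random, with 25 imputations.

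- **Step 1** is used when the missing pattern is not monotone: "the Markov Chain Monte Carlo (MCMC) method will be used to impute missing values by treatment". For scale, "the imputed values will be rounded to 3 decimals", in units of 10^9/L.
- **Step 2** fills in the rest: "The MONOTONE REG statement will be used with seed 2101703". Its predictors are given as "The missing values at each visit will be imputed based on treatment, values at baseline and previous visits, and prior TPO-receptor agonist use". Treatment is a covariate here, so one residual SD serves all arms.
- **Then** "the response will be defined based on platelet counts in the 25 complete datasets", and a logistic model is fitted to each dataset and pooled.

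SAP 8.1 counts a patient as a responder on meeting both criteria "at any visit during the treatment period and without a use of rescue medication". SAP 8.1.2 names no transformation, bounds or predictive-mean matching. The only rule for impossible values is in the hypothetical-strategy analysis of mean change (SAP 8.2.2): "When imputed value out of range (ie value <0), the value will be replaced by min value in dataset". That rule makes sense only if imputation is on the raw scale.

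**The concern.** Patients enter below 30,000/µL, the count cannot fall below zero, and the secondary endpoints reach 100,000/µL. If about half of the active patients respond, as the sample size assumes, the regression is fitted to a mixture of low non-responders and much higher responders. Its residual SD is then large compared with a non-responder's level. Each missing visit of a dropout receives a normal draw with that SD, and one draw above the threshold is enough to make the patient a responder.

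At stake is the only sensitivity analysis of the primary endpoint that changes the missing-data assumption. The other one in SAP 8.1.2 changes only the rescue-medication window. If its response rates are inflated by the imputation model, it is a poor check on the non-responder imputation of the primary analysis. With 12 placebo patients, one or two imputed responders matter.

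**Working it through.** **Inputs from the documents.** Arms of 24/24/12 and response of 50% against 1% (SAP 4.4). Entry count below 30,000/µL (SAP 2.1). Eight scheduled post-baseline visits: W1D4, W2D8, W3, W5, W7, W9, W11 and W12 (SAP Appendix 15.1). Neither document gives a platelet SD or a dropout rate, so both are assumptions below.

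**The plan's own figure.** The pooled p is (24 × 0.50 + 12 × 0.01)/36 = 0.3367. The null SE is √[0.3367 × 0.6633 × (1/24 + 1/12)] = 0.1671. The alternative SE is √(0.25/24 + 0.0099/12) = 0.1060. The continuity correction is ½(1/24 + 1/12) = 0.0625. Then z = (0.49 − 0.0625 − 1.96 × 0.1671)/0.1060 = 0.943, and Φ(0.943) = 0.827. The stated power reproduces and is not in dispute. It matters here only as the source of the 50% and 1% rates.

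**Closed form.** Take a non-responder with conditional mean μ = 15 (×10^9/L) and baseline 15, so that both criteria coincide at 30. With k missing visits and independent draws, P(at least one draw ≥30) = 1 − [Φ((30 − μ)/σ)]^k. For k = 4:

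- σ = 5: 1 − Φ(3.0)^4 ≈ 1%
- σ = 10: 1 − Φ(1.5)^4 = 24%
- σ = 15: 1 − Φ(1.0)^4 = 50%
- σ = 20: 1 − Φ(0.75)^4 = 64%

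**Simulation of step 2.** Sequential normal regression with posterior draws, 24/24/12 patients, 8 visits, dropout only among patients without a response so far, 400 trials × 5 imputations. Cells show the percentage of dropouts classed as responders: raw scale / log scale / truth.

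| Active rate; responder median (×10^9/L) | Mean dropouts of 60 | Residual SD | Placebo dropouts | Active dropouts |
|---|---|---|---|---|
| 50%; 60 | 24.3 | 29.4 | 54 / 23 / 1 | 66 / 36 / 19 |
| 50%; 60 | 11.8 | 27.8 | 47 / 19 / 0 | 61 / 32 / 18 |
| 50%; 45 | 9.2 | 13.3 | 24 / 10 / 0 | 37 / 22 / 18 |
| 50%; 45, less spread | 9.0 | 9.9 | 15 / 8 / 0 | 26 / 18 / 16 |
| 30%; 80 | 10.2 | 29.3 | 45 / 16 / 0 | 52 / 22 / 9 |
| 10%; 45 | 12.1 | 5.4 | 5 / 4 / 0 | 6 / 5 / 2 |
| 0% | 12.9 | 3.1 | 0 / 1 / 0 | 0 / 1 / 0 |

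In the four 50% rows, 10-26% of the raw-scale draws were negative.

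**Other assumed settings.**

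- Within-patient log-SD 0.35, a 5-fold rise in half of active patients, dropout 34% placebo and 19% active: 54% of placebo dropouts are converted raw, 18% log, 6% true. Placebo response is 29% raw, 17% log, 13% true. Active response is 64%, 57% and 55%. The treatment difference is about 34 points raw (35 from the rounded rates), 40 log and 42 true, a loss of up to about 8.
- Log-SD 0.20, about a third of placebo dropping out, true placebo rate 0.3% (near the planned 1%): 32% raw, 6% log, 0% true. Placebo response is 11.1% raw and 2.4% log.
- Log-SD 0.20, a 3-fold rise, 30% active response: 10% raw, 6% log.
- Dropout of about 10% placebo and 6% active: difference 44.0 true and 42.1 raw (log-SD 0.35, 5-fold rise), or 47.0 true and 45.9 raw (log-SD 0.25, 3-fold rise). The losses are 1.9 and 1.1 points.

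**Arm-level example** (30% active, median 80). Moving from non-responder to raw-scale imputation takes placebo from 0.9% to 10.1% (+9.2) and active from 27.9% to 36.4% (+8.5). The difference goes from 27.0 to 26.3 points. On the log scale the rates are 4.2% and 31.5%.

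**The case against.** The strongest reply is that the damage may be small. Protocol 1.4 intends patients who stop treatment to be followed for the planned study period, and this analysis uses counts obtained after discontinuation or rescue. Little may then be missing, and the difference moves by only 1 to 2 points. That stands as a limit on size, although Protocol 4.2.2 asks only for end-of-study assessments where possible. It is also fair that log-normal simulated data favour the log model, that only step 2 was simulated, and that step 1 runs by arm and so does not carry active-arm spread into placebo draws.

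A reader might infer several stronger things that the documents do not support:

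- **Every imputed responder is noise.** In active dropouts part of the imputed response is legitimate under missing at random: 16-19% truly respond later in the 50% rows.
- **Placebo is always inflated most, so a real effect will look fragile.** In the arm-level example the two arms rise almost equally. The asymmetry depends on who drops out.
- **SAP 8.2.2 needs the same change and its negative-value rule should go.** That endpoint is a mean change, with no threshold. With about 40% placebo dropout, raw imputation gave a placebo mean change of 0.7-1.0 against 0.9 true, while log imputation with back-transformation gave 2.1-2.5.
- **The missing negative-value rule in 8.1.2 is itself the fault.** A negative draw cannot meet the response criteria. At most it affects later visits as a predictor.

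**Conclusion.** The point holds for the treatment-policy response analysis in SAP 8.1.2. Normal imputation of raw counts, one residual SD over all arms and an any-visit threshold together inflate response in every arm. At the planned 50% active rate, roughly 15-55% of placebo dropouts are converted on the raw scale, against about 6-23% on the log scale and 0-6% in truth. With lower active response and low variability the raw figure is about 8-10%. It is about 5% at a 10% active rate and vanishes if almost nobody responds. The shift in the treatment difference is about 1 to 8 points, depending on assumed dropout, and is small with good follow-up after discontinuation.

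The direction follows from the text. The size rests on assumed spread, responder level and dropout. This is a supportive analysis: the primary comparison, with non-responder imputation and Fisher's exact test, is not affected.

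**What to change.** In SAP 8.1.2, for the response analysis only, state that both imputation steps use log platelet count, with log baseline as predictor (the TRANSFORM LOG facility of PROC MI). State also that values are back-transformed before the 30,000/µL and doubling criteria are applied. Because SAP 8.2.2 borrows its imputation from 8.1.2 by cross-reference, say there that the mean-change imputation stays on the raw scale and keeps its out-of-range rule.

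The cost is a few lines of text and one procedure statement before database lock, with no new data. The change relies on approximate log-normality, and a recorded count of zero would need a stated offset. It does not remove the excess, because the pooled residual SD and the any-visit rule remain. By-arm imputation or predictive-mean matching could be considered in addition, but neither was tested here. The report should give the number of patients with imputed visits, and of imputed responders, by arm.

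### The fallback imputation in SAP 8.1.2 treats three visit blocks separately, so a patient missing a whole later block appears to be imputed without the on-treatment counts from earlier blocks

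*SAP*

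**What the plan says.** SAP 8.1.2 (treatment-policy sensitivity analysis of platelet response) imputes missing counts up to Week 12 "under the missing at random (MAR) framework", giving 25 data sets in two steps. In step 1, "the Markov Chain Monte Carlo (MCMC) method will be used to impute missing values by treatment", to make the missing pattern monotone. In step 2, monotone regression fills the rest: "The missing values at each visit will be imputed based on treatment, values at baseline and previous visits, and prior TPO-receptor agonist use".

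The fallback follows: "If model fail to converge because the number of visits is more than number of subjects, the model will be reformed". The visits are cut into Week 1 Day 1 to Week 2 Day 8, Week 3 to Week 7, and Week 9 to Week 12. These blocks "will be imputed by two steps imputation procedures described above separately with unique seed", each with its own pair of seeds. The SAP does not say which predictors each block uses.

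SAP 8.2.2 uses the same method for change from baseline. The treatment-policy analysis there adopts the 8.1.2 imputation, and the hypothetical-strategy analysis repeats the trigger ("If model fail to converge because the number of visit is more than number of subjects") and points back to 8.1.2.

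**The concern.** The split exists to reduce the number of visits in one model. If earlier-block visits were still predictors in later blocks, the split would achieve little. The natural reading is therefore that the previous visits in step 2 now means previous visits in the same block.

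For a patient last seen at Week 7, all of Weeks 9 to 12 would then be drawn without any on-treatment count, although up to five post-baseline counts were observed (Day 4, Day 8, Weeks 3, 5 and 7). The SAP's main model uses that history.

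The direction matters because response needs only one qualifying count at any visit. Imputation cannot change a patient who has already responded. It can only convert patients who have not, and the counts being set aside are their low ones. Blocks drawn independently of each other also give extra chances to cross the threshold. At stake is how far these analyses can serve as robustness checks.

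**Working it through.** **1. Plan figure.** The documents give no number for the imputation and no dropout rate. The one stated figure that shares inputs with the check below is power (SAP 4.4: 24 vs 12 patients, 50% vs 1%, two-sided 5%, 82.74%). Using the pooled-variance normal approximation with continuity correction:
- pooled rate (12 + 0.12)/36 = 0.3367
- null SE √(0.3367 × 0.6633 × 0.125) = 0.1671
- alternative SE √(0.25/24 + 0.0099/12) = 0.1060
- correction 0.5 × (1/24 + 1/12) = 0.0625
- z = (0.49 − 0.0625 − 1.96 × 0.1671)/0.1060 = 0.943, so power is 82.7%. It reproduces.

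**2. Trigger.** The schedule of events has 9 platelet visits from Day 1 to Week 12 (Days 1, 4 and 8; Weeks 3, 5, 7, 9, 11 and 12). The smallest arm is placebo with 12 planned. Visits outnumber patients only if an arm has fewer than 9 usable patients.

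**3. Predictors of the Week 9 count for a patient last seen at Week 7.**
- Main model: treatment, baseline, prior TPO-receptor agonist use, Day 4, Day 8, Weeks 3, 5 and 7.
- Fallback, natural reading: treatment, baseline, prior TPO-receptor agonist use.

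Such a patient has a monotone gap, so step 2 fills it, not the by-arm MCMC step.

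**4. Simulation.** Trials of 24/24/12; 200-250 trials per scenario; 10 imputations each; monotone regression on the raw count scale with Bayesian parameter draws. Response is any visit with at least 30,000/µL and at least twice baseline. Assumptions, not in the documents: log-scale SD 0.15 or 0.3 between patients and 0.2 within; dropout 15% or 30%, either at random or only among patients not yet responding; last count at Week 3 or 7 unless stated. Block and full models both keep treatment, baseline and TPO-receptor agonist use. The full model adds all earlier visits; the block model adds only those in the same block.

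Selected scenarios at 30% dropout and between-patient SD 0.15, each cell block / full / true (%):

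| Assumed active vs placebo rate; dropout | Response imputed to not-yet-responding active dropouts | Active rate | Placebo rate | Difference |
|---|---|---|---|---|
| 50 vs 1; random | 68 / 26 / 5 | 59.0 / 52.1 / 48.7 | 12.6 / 7.2 / 1.8 | 46.3 / 44.9 / 47.0 |
| 50 vs 1; not yet responding | 74 / 32 / 6 | 60.2 / 53.3 / 49.1 | 14.7 / 9.1 / 1.9 | 45.6 / 44.2 / 47.2 |
| 50 vs 10; not yet responding | 73 / 30 / 5 | 60.1 / 53.1 / 49.1 | 24.1 / 17.5 / 11.0 | 36.0 / 35.6 / 38.0 |
| 20 vs 1; not yet responding | 48 / 11 / 2 | 31.0 / 22.0 / 19.7 | 11.4 / 4.8 / 2.3 | 19.6 / 17.2 / 17.4 |
| 1 vs 1; not yet responding | 5 / 1 / 0.4 | 3.3 / 2.1 / 1.9 | 4.0 / 2.2 / 2.0 | −0.7 / −0.1 / −0.1 |
| 50 vs 1; last count Week 9 or 11 | 17 / 9 / 1 | 51.3 / 50.1 / 48.8 | 5.7 / 4.4 / 2.2 | 45.6 / 45.7 / 46.6 |

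Over all scenarios with 50% active response and last count at Week 3 or 7, the first column runs 66-74% by block, 24-32% with full history and 5-7% true; the placebo equivalents are 40-49%, 19-26% and about 1-2%. Removing baseline as well moved the active block figure by only about 1 point in those scenarios.

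**5. Odds ratio.** SAP 8.1.2 analyses the imputed data by logistic regression. Crude odds ratios from the table:
- first row: block (0.590/0.410)/(0.126/0.874) = 10.0; full (0.521/0.479)/(0.072/0.928) = 14.0
- third row: block (0.601/0.399)/(0.241/0.759) = 4.7; full (0.531/0.469)/(0.175/0.825) = 5.3
- fourth row: block (0.310/0.690)/(0.114/0.886) = 3.5; full (0.220/0.780)/(0.048/0.952) = 5.6

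In these rows the block method pulls the odds ratio towards 1.

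**6. Change from baseline (rough, not simulated).** Ignoring baseline, with equal SDs at both visits and visit correlation ρ, the block draw exceeds the history-based mean by ρ × (arm mean − last count) per dropout. Assume means of 60,000 active and 20,000 placebo, last count 12,000 in both, dropout 15-30% in both, ρ = 0.5-0.85. The difference between arms shifts by dropout × ρ × (48,000 − 8,000): from 0.15 × 0.5 × 40,000 = 3,000 to 0.30 × 0.85 × 40,000 = 10,200/µL. Cancellation between arms should therefore not be assumed for this endpoint under missing at random.

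**The case against.** Several objections have force, and they rule out stronger readings that a reader might infer.

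- **That later counts come simply from the arm's distribution.** They do not: the fallback reuses the two-step procedure, whose step 2 keeps baseline, treatment and prior TPO-receptor agonist use. A single-patient calculation from an assumed arm distribution (mean 60,000, SD 45,000, hence 75% at or above 30,000) omits baseline and the doubling rule, so it is not the SAP's model.
- **That the SAP expects the main model to fail.** The wording is conditional, and the planned numbers do not meet it. The trigger is not idle, though. In the placebo-based step of 8.2.2, a Week 12 regression on seven earlier post-baseline visits, baseline, TPO-receptor agonist use and an intercept has 10 parameters. Two missing Week 12 counts among 12 patients leave no residual degrees of freedom, although visits do not outnumber patients.
- **That missing at random is broken.** The imputation is still of that type. It conditions on less, which makes the assumption stronger and less plausible.
- **That the treatment effect is exaggerated.** On response, both arms rise, the difference hardly moves, and the crude odds ratio falls where the drug works. Part of the excess over truth also occurs with full history, from normal imputation of skewed counts.

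The SAP also does not expressly exclude earlier-block visits, so the sponsor may intend otherwise. Protocol 1.4 says patients who discontinue treatment are followed for the planned duration, which would leave fewer gaps. Protocol 4.2.2 is less definite.

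**Conclusion.** The point holds within limits. If the fallback is used as written, the natural reading discards observed on-treatment history for patients missing a whole later block, and with an any-visit endpoint this tends to overstate imputed response among dropouts who have not yet responded. The block figure was higher than the full-history figure in every scenario tried, but its size rests on assumed dropout, variability and response rates. It shrinks to 17% vs 9% for dropout within the last block and 5% vs 1% for an ineffective drug.

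The consequence is mainly for the arm response rates in a sensitivity analysis. The primary analysis of response uses non-responder imputation and is unaffected. For change from baseline the effect on the contrast could be larger, but only the rough illustration above supports that. This is a cheap improvement, not a threat to the main result.

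**What to change.** In SAP 8.1.2, list the predictors for each block: treatment, baseline count, prior TPO-receptor agonist use and earlier visits in the same block. For the second and third blocks, add the patient's last count (or mean count) from the preceding block. Run the blocks in order within each imputed data set, so that the carried value is always available. The cross-reference in 8.2.2 then picks up the change.

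The cost is SAP wording, minor programming and one extra predictor in each of the two later blocks. It stays affordable: the placebo-based Week 12 regression would have 6 parameters (Weeks 9 and 11, carried count, baseline, TPO-receptor agonist use, intercept), against 10 with full history. The simulation compared blocks with full history; a single carried count was not simulated separately and may recover only part of the gain.
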